10 TRANSLATIONAL STUDIES

1. Targeted Cell Surface Analysis

Radiation can alter the cell surface expression of many immunomodulatory proteins. Upregulation of PDL1 and PDL2 has been demonstrated in multiple cell lines. Altered expression of MHC 1 on tumor cells has also been reported. Changes in the composition of the immune regulatory cells within the tumor micro-environment in response to changes in tumor cell phenotype has also been demonstrated. Utilizing paired pre-XRT (biopsy) and post XRT (surgical specimen) tumor tissues and normal tissue samples from the resection sample, we will use immunohistochemistry to assess cell surface markers and immune parameters. Tumor panels will include PDL1, PDL2, HCA2, IDO, HC10, B2m, Calreticulin, MHC-1, Fas, ICAM. T-cell panels will include CD3, CD8, FoxP3, TBet, Ki67, GranzymeB; and CD3, CD8, PD1, 1263 Tim3, Lag3, GranzymeB.

2. Tumor Immune Microenvironment

Using the “biopsy-XRT-resection” approach, we will be able to gain insight into the composition of the tumor immune microenvironment before SBRT and understand how SBRT influences the microenvironment and expression of immunotherapy targets. Prior rodent studies have delineated how radiation dose and fractionation can alter the STING pathway.^{23, 24, 25} The consequence of this is recruitment and activation of dendritic cells which can prime CD8+ T cells and mediate a systemic cytotoxic tumor response.²⁶ Similarly, other groups have utilized murine models to delineate how radiation can increase the CD8/CD4 ratio and broaden the T-cell repertoire (Ko et al IJROBP 2019).²⁷ We propose to examine changes in the tumor immune microenvironment focusing on transcriptomic changes as well as functional changes in the T-cell receptor repertoire.

3. Gene Expression Profile

We will use the NanoString nCounter® PanCancer ImmunoOncology (IO) 360™ Gene Expression Panel to perform quantitative highly multiplexed gene expression profiling. Total DNA and RNA will be collected from FFPE-embedded biopsy (pre-radiotherapy) and surgical (post-radiotherapy) specimens using the AllPrep DNA/RNA FFPE Kit (Qiagen). DNA will be cryopreserved for future translational genomic studies. RNA will be analyzed on the nCounter® PanCancer IO 360™ Gene Expression Panel using the instrumentation in the Clinical Molecular Oncology Laboratory (CMOL) overseen by [name] at KU Cancer Center. This platform quantifies expression levels for 770 transcripts, including 40 housekeeping genes for automated normalization, and provides a quantitative measure of immune-related biological signatures, pathways, and processes, extrapolated relative levels of immune cell subtypes, and expression of immunotherapy targets within each sample. Paired analysis between pre-radiotherapy and post-radiotherapy samples will enable us to detect radiotherapy induced changes in the tumor immune microenvironment and expression of immunotherapy targets.

These studies will provide critical insight into the potential of radiotherapy as an immunogenic adjunct in NSCLC and identify novel therapeutic approaches to combine radiotherapy with immunotherapy.

4. Radiation-Mediated Changes in T-cell Repertoire in Tumor Tissue

We will use the AmpliSeq™ for Illumina® Direct FFPE DNA to develop a highly multiplexed targeted resequencing panel followed by DNA sequencing in order to measure T cell diversity and clonal expansion by sequencing T cell receptor (TCR) beta chain rearrangements. Paired pre-RT core needle biopsy and post-RT resected tumors will be compared for unique immune cell receptor transcripts that

have infiltrated tumor tissue after radiation treatment. This project will lay the groundwork for future work to identify radiation treatment regimens that may be augmented with immune-therapeutics.

5. Radiation-Mediated Changes in T-cell Repertoire in Peripheral Blood

We will process peripheral blood T cells in order to measure T cell diversity and clonal expansion by sequencing TCR beta chain rearrangements. We will simultaneously evaluate T cell profile by flow cytometry, assessing for markers of T cell exhaustion.

6. Tumor Tissue and Circulating Tumor Cell Analysis

Circulating tumor cells (CTCs) have been widely used for diagnostic purposes as well as a biomarker to screen for treatment failure. Furthermore, CTCs have been shown to prognosticate both lung and head/neck squamous cell carcinoma patient disease-free survival and contribute to both loco-regional and distant metastasis.^{28,29,30,31} In our model system, we have previously demonstrated that radiotherapy can induce accelerated tumor repopulation in vivo and this is likely regulated by epithelial-to-mesenchymal transition (EMT).^{32,33} Predictably, generation of “mesenchymal” CTCs require EMT and those CTCs with persistent EMT pathway activation have been correlated as a poor patient prognostic outcome particularly in head and neck cancer.^{34,35} In addition, EMT gene expression in CTC’s from lung cancer patients who undergo curative surgical resection have been shown to be a poor prognostic feature.³⁶ Furthermore, PD-L1 expression (and other immunomodulatory proteins) are known to be upregulated in pre-clinical models^{37,38} following radiotherapy and immune cell surface proteins (i.e. PD-L1) has been shown to be expressed in CTCs.³⁹

We propose to examine CTC before and after SBRT. Both mesenchymal and nonmesenchymal (epithelial) expressing CTCs will be isolated from whole blood using specialized nanofabricated cell isolation chips (KU Lawrence collaboration, [name], [name]) designed for harvesting CTCs and demonstrate a 10-100x higher cell capture rate compared with commercial vendors.⁴⁰ Endpoints include mesenchymal and epithelial CTC cell enumeration before and after SBRT; examination of PD-L1 cell surface expression in CTCs; as well as targeted transcriptomic analysis of collected CTCs using a modified Nanostring nCounter® PanCancer Progression Panel customized with supplemental user-defined genes focusing on p38-MAPK pathway.

We hypothesize from this work that following SBRT there will be a higher proportion of mesenchymal CTCs over epithelial CTCs and these results will be confirmed using targeted transcriptomic analysis. We also anticipate that patients receiving SBRT will have upregulation of PDL1 cell surface expression and will be confirmed by immunofluorescence. We also hypothesize that genes in the p38-MAPK pathway will be upregulated following SBRT and promising genes candidates will be confirmed by immunohistochemistry looking at tumor tissue before and after SBRT. The goal of this work will be to: 1) explore the effect of SBRT on mesenchymal CTC generation; 2) examine the gene expression profile of CTCs with a focus on EMT; and 3) identify promising novel targets within the MAPK pathway that are up-regulated following SBRT that maybe relevant and targetable for metastasis.

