3 OBJECTIVES AND ENDPOINTS

3.1 Primary Objective

Assess the impact of non-ablative SBRT (800 cGy X 3 fractions) on immunomodulation in NSCLC tumor cells through analysis of targeted cell surface, tumor immune microenvironment, gene expression profile, radiation mediated changes in T-cell repertoire in tumor tissue and peripheral blood and circulating tumor cell surface expression.

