4 STUDY DESIGN

4.1 Overall Design

This is a single arm pilot study. Participants with medically operable NSCLC will receive SBRT 800 cGy X 3 fractions delivered 5-7 days prior to planned surgery.

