8.2 Sample Procurement

8.2.1 Pre-SBRT Biopsy Sample

Pre-SBRT biopsy samples will be obtained at time of diagnostic biopsy and will consist of a minimum of two core biopsies.

- **Required collection of archival tumor biopsy tissue (either from initial diagnosis of lung cancer done prior to any study intervention or from any subsequent biopsy), for translational studies.**
A formalin-fixed paraffin-embedded (FFPE) tumor specimen in a paraffin block (preferred) or at least 15 slides containing unstained, freshly cut, serial sections should be submitted along with an associated pathology report prior to study enrollment. If only 10 to 14 slides are available, the specimen may still be used, after Principal Investigator confirmation has been obtained.
- **Required fresh tumor biopsy for translational studies.**
If archival tumor tissue is unavailable or is determined to be unsuitable for required testing, if participant consents, then fresh tumor tissue can be obtained from a biopsy performed after screening.

If participant does not consent, they cannot participate in this study.

Refer to Lab Manual for additional information on tumor specimens collected at screening.

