8.2.2 Surgical Sample

Post-assessment by pathologist and verification that adequate tissue has been obtained for clinical use, the remainder of the tumor tissue will be processed for translational studies as defined in study laboratory manual.

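### Item 4 of the translational studies describes T-cell receptors found by comparing biopsy with resection as having infiltrated after radiation, but absence from a small core biopsy does not show absence before SBRT

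*Protocol*

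**What the plan says.** Section 10, item 4, plans sequencing of T-cell receptor beta rearrangements in FFPE tissue. It then states the comparison: "Paired pre-RT core needle biopsy and post-RT resected tumors will be compared for unique immune cell receptor transcripts that", and the sentence continues after a page break, "have infiltrated tumor tissue after radiation treatment". The item's title attributes the changes to radiation.

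The pre-treatment specimen "will consist of a minimum of two core biopsies" (section 8.2.1). It is submitted "in a paraffin block (preferred) or at least 15 slides", and 10 to 14 slides can be accepted with confirmation. For the resection, "the remainder of the tumor tissue will be processed for translational studies as defined in study laboratory manual" (section 8.2.2). Section 4.1 says "This is a single arm pilot study". The primary objective (section 3.1) includes "radiation mediated changes in T-cell repertoire in tumor tissue and peripheral blood". Section 2 makes the analysis descriptive, without formal testing.

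**The concern.** Item 4 joins a comparison of two samples to a conclusion about timing and cause. Two limited samples of one unchanged T-cell population never contain the same list of rare clonotypes. Some will always appear in the second sample and not in the first. If that list is reported as cells that arrived after radiation, ordinary sampling turnover is published as a treatment effect within a named component of the primary objective. The lack of formal testing does not help, because the fault lies in the attribution and not in a p-value.

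**Working it through.** The protocol gives no clonotype count, T-cell yield, template number or sequencing depth, so it has no figure of its own to reproduce.

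**Assumed inputs.** S = 2,000, 10,000 or 50,000 clonotypes. Clone frequencies p_i are proportional to i^(-a), with a = 0.8, 1.0 or 1.2. Each sample has n = 1,000, 5,000 or 20,000 T cells. The repertoire is the same before and after, that is, no SBRT effect.

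**Step 1: chance that the core misses a clone already present.** This is (1 - p)^n.
- p = 0.1%: 0.999^500 = 61% and 0.999^1000 = 37%.
- p = 0.01%: 95% and 90% for the same two sample sizes.
- p = 1%: 0.99^500 = 0.7%.

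**Step 2: share of resection clonotypes that look new at equal depth.** With m_i = (1 - p_i)^n, the expected share is approximately Σ m_i(1 - m_i) / Σ (1 - m_i). Over the nine repertoires:

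| T cells per sample | Lowest | Highest |
|---|---|---|
| 1,000 | 58% (S = 2,000, a = 1.2) | 87% (S = 50,000, a = 0.8) |
| 5,000 | 26% (S = 2,000, a = 0.8) | 78% (S = 50,000, a = 0.8) |
| 20,000 | 2% (S = 2,000, a = 0.8) | 64% (S = 50,000, a = 1.0) |

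Simulation gives the same ranges. As a share of resection T cells instead of clonotypes, it gives 18-77%, 8-59% and 1-40%. Adding an assumed 25% between-sample CV in clone frequency changes the clonotype shares to 59-88%, 27-79% and 3-65%.

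**Step 3: the reverse direction.** At equal depth the biopsy-only share is about the same. For S = 10,000, a = 1.0 and 1,000 templates each, 73% look new and 72% look lost. With a 25% CV, new minus lost, as a fraction of resection clonotypes, averages -0.011 to +0.015 by count. By template share it averages -0.004 to +0.005. With the same repertoire but 1,000 core and 10,000 resection templates, 88% look new and only 35% look lost. Unequal depth therefore makes the error one-sided, but equal depth does not remove it.

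**Step 4: if the resection is read deeper.** The protocol does not say that it is. At an assumed 5 to 20 times the depth (25% CV) and no SBRT effect:
- Richness is multiplied by 2.6-12.8, 1.4-8.8 and 1.0-6.8 at the three core sizes.
- Shannon diversity is multiplied by 1.06-1.30, 1.01-1.18 and 0.99-1.09.
- The Simpson index is multiplied by 0.99-1.01.
- Normalised clonality, 1 - H/ln R (H Shannon diversity, R richness), generally rises. For S = 10,000, a = 1.0 and a 1,000-cell core, without added CV, it goes from 0.13 to 0.19 at 5 times and 0.24 at 20 times.

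**Step 5: large clones.** A clone truly at 0.5% is missed with probability 0.995^1000 = 0.7%, and practically never at 5,000 cells. If size is judged from the resection count (5 or more of 1,000), up to 1.3 such clones per pair look falsely new at 1,000 cells with a 25% CV. None do at 5,000 or 20,000.

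**Step 6: what an excess of new over lost could mean.** Suppose the core comes from one of four tumour regions and 10-50% of T cells are region-specific (assumed). Then the excess with no SBRT effect is +0.02 to +0.28 by template share. If 20% of resection T cells are truly new, it is +0.09 to +0.16. The two ranges overlap. The count version equals resection richness minus biopsy richness, so it can even fall, to -0.14 to -0.18, when the 20% come from ten large clones.

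**The case against.** The strongest reply is that item 4 states no presence/absence rule. The clause may only name what is being sought, and the sentence before it lists diversity and clonal expansion, which do not rest on presence or absence alone. Item 5 also sequences blood, drawn before SBRT and before surgery, and item 1 stains paired tissue for CD3 and CD8. Part of this stands: the item is wider than the clause, and those data can say something about infiltration. But they do not show which tumour clonotypes were absent before SBRT. If only an aim was meant, rewording loses nothing.

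A second reply is that the laboratory manual may match input. It may, but step 2 already assumes equal depth.

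Third, every size here is assumed, and the range reaches down to 2%. That is correct. It supports the direction of the error, not one number.

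A reader might also infer that the artefact mimics an effect the trial predicts, because item 2 says that "radiation can increase the CD8/CD4 ratio and broaden the T-cell repertoire". The documents do not support that. The statement is background from murine models, and section 2 hypothesises alterations without a direction. The indices also disagree: greater depth raises richness, which reads as broadening, while clonality generally rises too, which reads as narrowing. Nor does the protocol say that the resection will be read more deeply.

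Finally, causal wording in a single-arm trial is not special to item 4, since item 3 uses it too. What is particular here is the reliance on non-detection in a small sample.

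**Conclusion.** The point holds, as a minor one. The written reading, that receptors distinguishing resection from core arrived after radiation, does not follow from the two specimens, and matching the input would not rescue it. Under the assumed repertoires, the share of resection clonotypes that look new without any SBRT effect runs from 2% to 87%. Only combinations of few clonotypes and high T-cell yield give small values. Clones at about 0.5% or more and the Simpson index are little affected, though at 1,000 cells even large clones need some caution. It would go too far to say that the tumour repertoire work is uninformative, or that a depth-matched excess of new clonotypes would establish infiltration; step 6 argues against the second. The consequence is confined to one clause in one of six translational items, in a descriptive pilot of 10.

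**What to change.** 1. In item 4, replace the closing clause (*that* followed by "have infiltrated tumor tissue after radiation treatment") with *detected in the resection but not in the biopsy*. Describe the result as a biopsy-to-resection difference not attributable to SBRT alone. This is the only change this text must have.
2. Here or in the analysis plan, down-sample each pair to the smaller number of TCR-beta templates before comparing richness, diversity or clonality, and report both template numbers.
3. At matched depth, report resection-only beside biopsy-only clonotypes for each participant, by count and by template share, so that the resection-only list is not read alone. Treat an excess of new over lost as descriptive, because regional differences within the tumour can produce a similar excess. Report clones at about 0.5% or more separately, as the more robust comparison.

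The cost is one reworded clause and a standard computing step, with no added tissue, visits or tests. Some resection depth is discarded, and rare clones are not individually called infiltrating. Single pairs stay noisy. At 1,000 cells with a 25% CV and no SBRT effect, the 95% range of new minus lost is about ±0.22 by count and ±0.09 by template share. For a mean of 10 pairs it is about ±0.06 and ±0.03.

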11 ADVERSE EVENTS/SERIOUS ADVERSE EVENTS

Although pregnancy is not always serious by regulatory definition, for the purposes of this protocol, this is considered to be an SAE and follow the SAE reporting timeline.

Refer to Appendix B for additional Adverse Event/Serious Adverse Event information.

11.1 Adverse Event Monitoring

Baseline adverse events are recorded and graded using NCI Common Terminology Criteria for Adverse Events (CTCAE) version 5.0⁴¹. Additional serious adverse event and adverse event monitoring begins after initiation of study intervention and ends 36 months following surgery (i.e.; end of study).

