Diagnosis and Main Inclusion Criteria	
Inclusion Criteria:
 
 • Stage I-II NSCLC • Adequate diagnostic biopsy tissue to allow pre-SBRT tumor analysis • Candidate for oncologic surgery (lobectomy or sub lobar resection) for the lung cancer • Lesion located peripherally, ≥ 2 cm from bronchial margin, and 1 cm from visceral pleura, with location deemed acceptable by cardio-thoracic surgeon for resection. • Adequate pulmonary function test results 
Exclusion Criteria:
 
 • Prior history of lung/chest wall surgery • Prior chest radiation • Prior immunotherapy • History of autoimmune disease • Currently using immunosuppressive drugs
Study Product(s), Dose, Route, Regimen	SBRT 800 cGy x 3 fractions

Duration of Administration
	
Total: 4-5 days
 
1-2 days - consultation and simulation
 
3 treatment (study intervention) days
 
Study intervention (SBRT) delivery will be scheduled for 3 consecutive days, but may be modified as needed by the treating radiation oncologist.

Interim Monitoring
	
The data safety monitoring committee (DSMC) of The University of Kansas Cancer Center is responsible for monitoring participant safety for this trial.

Statistical Methodology
	
We will summarize peri- and post- operative surgical complication rates as well as tumor control outcomes using descriptive statistics.
 
Peri- and post- operative surgical complication rates will be quantified using the Clavien-Dindo classification of surgical complications ^{1,2}.
 
Wound healing complication rates will be scaled as defined by the General Thoracic Surgery Database. ³

Stopping Rules
	
If a participant experiences one or more of the following events, possibly related to study intervention, study will be suspended pending DSMC review to determine if study should continue.
 
 a. Wound healing delay beyond standard timeframe as deemed by study Cardio-Vascular (CV) surgeons b. Peri operative/post-operative surgical complications beyond acceptable institutional rates as determined by study CV surgeons c. Death from study intervention

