9.1.1 Procedures During Study Intervention

Day 0 - Simulation

- Radiation Simulation
- Adverse event assessment

Day 1 – Prior to 1st fraction

- Blood collection for translational studies

Day 1 – 1st Fraction

- Radiation – Fraction 1
- Adverse event assessment

Day 2 – 2nd Fraction

- Radiation – Fraction 2
- Adverse event assessment

Day 3 – 3rd Fraction

- Radiation – Fraction 3
- Adverse event assessment

NOTE: There is a 5-7 day rest period after radiation and before surgery.

Day of Surgery (Occurs during days 8-10)

- ECOG
- CBC with Differential (± 3 Days)
- CMP (Serum Chemistries) (± 3 Days)
- Physical exam
- Adverse event assessment
- Peri-operative surgical complication assessment
- Blood collection for translational studies BEFORE surgery
- Surgical specimen collection

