11.2 Adverse Event Reporting

Information for adverse events, whether reported by the participant, directly observed or detected by physical examination, laboratory test or other means, will be collected, recorded, followed and reported in the CRIS system within 5 days of being reported.

All adverse events experienced by participants will be collected. Medical conditions are collected as baseline adverse events and evaluated as above. Additional adverse event monitoring begins after initiation of study intervention and ends 36 months following surgery.

Participants who experience an ongoing adverse event related to study intervention beyond 36 months will continue to be contacted by a member of the study team until the event is resolved, stabilized, or determined to be irreversible by the Sponsor/Investigator.

Study participants should also be instructed to report any new serious post-study event(s) that might reasonably be related to participation in this study.

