Appendix B: Reportable Events

Adverse Event (AE) Definition

Adverse event (AE) is defined as any new untoward medical occurrence or worsening of a preexisting medical condition in a clinical investigation participant administered study intervention and that does not necessarily have a causal relationship to this intervention. An AE can therefore be any unfavorable and unintended sign (such as an abnormal laboratory finding), symptom or disease temporally associated with the use of study intervention, whether or not considered related to the study intervention.

Progression of the cancer under study or events which are unequivocally due to disease progression should not be reported as an AE during the study unless the treating investigator considers it to be study intervention related.

Serious Adverse Event (SAE) Definition

A Serious Adverse Event (SAE) is any untoward medical occurrence that at any dose:

- Results in death.
- Is life-threatening (defined as an event in which the participant was at risk of death at the time of the event; it does not refer to an event which hypothetically might have caused death if it were more severe).
- Requires inpatient hospitalization or causes prolongation of existing hospitalization.
- Results in persistent or significant disability/incapacity.
- Is a congenital anomaly/birth defect
- Is an important medical event defined as a medical event or multiple medical events that may not be immediately life-threatening or result in death or hospitalization but, based upon appropriate medical and scientific judgement may jeopardize the participant or may require intervention (e.g., medical, surgical) to prevent one of the other serious outcomes listed above.
- Suspected transmission of an infectious agent (e.g., pathogenic or nonpathogenic) via the study intervention.

Although pregnancy is not always serious by regulatory definition, for the purposes of this protocol, this event is considered to be an SAE and follow the SAE reporting timeline.

Any component of the study endpoints that is considered related to study therapy should be reported as an SAE (e.g., death is an endpoint, if death occurred due to anaphylaxis, anaphylaxis is reported an SAE.)

NOTE: The following hospitalizations are not considered SAE's:

- An Emergency room or other hospital department visit <24 hours that does not result in admission. Unless considered an important medical or life-threatening event)

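### The AE/SAE window opens only at SBRT, so it is unclear whether a serious complication of the fallback research biopsy triggers expedited reporting, and the Day 0 assessment precedes the window

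*Protocol*

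**What the plan says.** **Start of monitoring.** Protocol section 11.1: "Additional serious adverse event and adverse event monitoring begins after initiation of study intervention", with the end set at 36 months after surgery. Section 11.2 gives the same start for AEs: "Additional adverse event monitoring begins after initiation of study intervention and ends 36 months following surgery". Appendix B repeats the start for both AEs and SAEs. Before that point, section 11.1 has baseline adverse events recorded and graded by CTCAE version 5.0, and section 11.2 links that category to medical conditions.

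**What counts as an AE.** Appendix B defines it as an occurrence "in a clinical investigation participant administered study intervention".

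**What study intervention means.** The Protocol Summary states: "Study intervention (SBRT) delivery will be scheduled for 3 consecutive days". It lists "1-2 days - consultation and simulation" as a separate line from the three treatment days, and attaches the study intervention label only to those three days.

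**Fresh biopsy.** Section 8.2.1, repeated in section 9.1, provides that if archival tissue is missing or unsuitable and the participant agrees, "then fresh tumor tissue can be obtained from a biopsy performed after screening". A participant who declines cannot enter the study. The stated purpose is translational research.

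**Day 0.** The first entry in section 9.1.1 is "Day 0 - Simulation", with an adverse event assessment listed under it. The schedule in section 9.3 marks the same assessment.

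**The concern.** The window opens at the first fraction, but for some participants the protocol requires an invasive research procedure before then. If that procedure causes serious harm, site staff reading sections 11.1 and 11.2 and Appendix B would find that monitoring has not started and that the event does not fit the AE definition. The natural place to enter it is the baseline record, where a complication of a study procedure would look like part of the patient's history. Whether the 24-hour report is due, and whether the DSMC sees the event, would depend on how each reader resolves the text.

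Separately, an AE assessment is scheduled at a visit that comes before AE monitoring is said to begin. The protocol does not say whether a finding at that visit is a baseline event or a reportable one.

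**Working it through.** No arithmetic applies and the plan gives no figure to reproduce. The check sets the passages against the participant's timeline.

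1. **Consent and screening.** The section 9.3 entry for adverse events is a medical history review only.
2. **Fresh biopsy, if archival tissue cannot be used.** It is done after screening (sections 8.2.1 and 9.1). It supplies the pre-SBRT sample, so it must come before the first fraction. Section 9.3 lists only archival tissue at screening, and no AE assessment is tied to a fresh biopsy.
3. **Day 0, simulation.** An AE assessment is scheduled (sections 9.1.1 and 9.3).
4. **Day 1, first fraction.** On the Protocol Summary's use of the term, study intervention starts here, and so does the window in sections 11.1, 11.2 and Appendix B.

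Steps 2 and 3 both fall before the stated start. The start rule appears in three places, so it is not a slip in one sentence.

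Does another clause cover step 2?

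- **Baseline recording (11.1, 11.2).** The event could be captured and graded, but as a baseline item.
- **SAE reporting (11.3).** It applies whatever the expectedness or relationship and has no start date of its own. It could be read to include the biopsy. Against that, section 11.1 and Appendix B expressly start SAE monitoring after initiation of study intervention.
- **Attribution scale (Appendix B).** Every category concerns the relationship to study intervention; none concerns a study procedure.
- **DSMC remit (section 14).** It is worded for participants receiving study intervention. Someone harmed by the biopsy who never reaches SBRT is not clearly inside it.
- **Unanticipated Problem (Appendix B).** The definition reaches research procedures, but only for unexpected events, and the protocol sets out no reporting route specific to it.
- **Risk section (1.3.1).** Neither a biopsy risk nor a biopsy visit is listed.

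No clause gives an explicit rule for a serious procedure-related event between consent and the first fraction. Some clauses point towards reporting and others away from it.

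**The case against.** The strongest reply is that such an event would not be lost. Baseline events are recorded and CTCAE-graded, monitoring after SBRT starts is described as additional to that, and section 11.2 says that all adverse events are collected. Section 11.3 sets no start date, and the wording about participants given the intervention sits in the AE definition, not in the SAE definition. This stands in part. A reader might infer that harm from the biopsy falls outside reporting altogether, and the documents do not support that. They support only that the route is unclear for a serious event.

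The second reply concerns Day 0. The heading of section 9.1.1 places simulation among procedures during study intervention, and the Protocol Summary counts consultation and simulation within the total duration of administration. On that reading Day 0 is inside the window. The assessment could also serve as the baseline, and might pick up a biopsy complication that is still present. This too stands in part: the text is ambiguous rather than flatly contradictory. But the same Protocol Summary entry separates simulation from the study intervention days, so the passages still need reconciling. Settling Day 0 alone would not bring the earlier biopsy into the window.

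The third reply is that the biopsy is only a fallback. Adequate diagnostic tissue is an inclusion criterion, and section 8.2.1 expects the pre-SBRT sample to come from the diagnostic biopsy. This stands in full as a limit on size. For those who do need a fresh biopsy, however, it is a condition of entry.

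**Conclusion.** The point holds as a gap in the safety-reporting rule. Followed as written, sections 11.1, 11.2 and Appendix B give weaker capture of harm from a protocol-specified research procedure than of harm from SBRT. A serious complication of the fallback biopsy would at most be recorded as a baseline event, without clearly triggering 24-hour reporting or DSMC review. The Day 0 assessment sits before the stated start.

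The size is small and cannot be put as a probability. Enrolment is 10, and the number needing a fresh biopsy could be anywhere from none upwards. A reader might be tempted to multiply an assumed number of biopsies by a general complication rate. The documents give neither figure, and a rate for all complications would in any case overstate the matter, because non-serious events can still be recorded at baseline. No efficacy result is affected: the primary endpoint is measured on tissue and blood, and the surgical and wound-healing endpoints start at surgery.

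The conclusion assumes that study intervention means SBRT delivery, as the Protocol Summary uses it. If the sponsor means it to include simulation, the Day 0 part falls away and the biopsy part remains. Label: cheap improvement.

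**What to change.** In section 11.1, section 11.2 and the monitoring paragraph of Appendix B, state two start points: from consent for AEs and SAEs related to study-specific procedures (fresh biopsy and simulation), and from the first fraction for all AEs and SAEs. Align the AE definition in Appendix B so that it covers events caused by those procedures, and let the attribution scale record a relationship to a study procedure. The Day 0 assessment then has a defined purpose, and section 11.3 and the DSMC review apply without interpretation.

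The cost is about a sentence in each of three places plus the adjusted definition, and a few more events to report. No treatment, visit or endpoint changes.
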